In 10 mg/kg once weekly cohort, the SMC will evaluate overall safety data when all 6 evaluable subjects have completed a minimum 4-week treatment period, and after 12 weeks of observation has been completed for all subjects enrolled in this cohort (see Section 2.1).

See Section 5.1.2.1.2 and Figure 5-3 for further details of the dose escalation algorithm, and Section 5.2.2 for a discussion of the rationale for dose selection.

Subjects will not be replaced unless the subject does not fulfill the requirement for dose determination. Dose determination is achieved when the subject receives 2 doses of avelumab at the scheduled regimen and completes the minimal 21-day safety observation period (DLT observation period) unless they discontinue due to a DLT. For the definition of a DLT, see Section 7.4.1.1.

The design of the dose escalation is based on Studies EMR100070-001 and EMR100070-002 and therefore allows for the ethnic sensitivity of avelumab to be evaluated across studies.

The overall study design is shown in Figure 5-1.

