### 5.1.2.1.2 Dose Escalation Scheme

Subjects will receive avelumab by IV infusion over 1 hour once every 2 weeks. Dose escalation of avelumab will be performed according to the following dose levels, representing a 3.3 or 2 times increase at each escalation. Each subject will receive a fixed dose of avelumab according to their allocated dose level:

- 3 mg/kg
- 10 mg/kg
- 20 mg/kg

The dose escalation criteria are as follows:

For each dose level, DLTs (as defined in Section 7.4.1.1) will be assessed during the 21 days after administration of avelumab. The criteria for moving from 3 mg/kg to 10 mg/kg of avelumab is if no subject experiences a DLT in the first 3 subjects. No additional 3 subjects will be enrolled. If 1 out of the first 3 subjects in the 3 mg/kg cohort experiences a DLT, this cohort will be expanded to 6 subjects. If  $\geq 2$  out of 3 or 6 subjects in the 3 mg/kg cohort experience a DLT, the study will be placed on hold. See also Section 2.1.

[figure not shown]
In the 10 mg/kg once every 2 weeks cohort, 6 slots will be opened at the same time for competitive enrolment of 6 subjects. If less than 2 out of the 6 subjects in this cohort experience a DLT, the dose of 10 mg/kg will be considered safe in Chinese subjects. If 2 or more subjects experience a DLT, the study will be placed on hold.

After completion of the 10 mg/kg once every 2 weeks cohort, the dose of avelumab will be escalated to 20 mg/kg once every 2 weeks in order to characterize the safety and PK of avelumab at a higher dose level. The criteria for moving from 10 mg/kg to 20 mg/kg of avelumab is if less than 2 out of 6 subjects experience a DLT at the 10 mg/kg dose level (once every 2 weeks cohort). Staggered “3 + 3” enrolment will be used for the 20 mg/kg cohort. If no subject experiences a DLT in the first 3 subjects, the avelumab dose level at 20 mg/kg once every 2 weeks will be regarded as safe in Chinese subjects; the additional 3 subjects will be enrolled to fill up the cohort for PK evaluation, but they will not be subjected to further DLT evaluation.

If 1 subject in the first 3 subjects experiences a DLT (confirmed by SMC only), an additional 3 subjects will be enrolled. If less than 2 out of the 6 subjects experience a DLT, the dose of 20 mg/kg will be considered safe in Chinese subjects. If  $\geq 2$  out of 3 or 6 subjects experience a DLT, the 20 mg/kg cohort will be put on hold (the decision will be made by SMC).

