**Figure 5-3 Dose Escalation Algorithm for Doses up to 20 mg/kg of Avelumab**

DLT: dose-limiting toxicity; Q2W: every 2 weeks; QW: every week.

At the conclusion of the 21-day DLT observation period for each cohort (excluding 10 mg/kg once weekly cohort), a data review will be conducted. The SMC (including Principal Investigators), is responsible for making dose escalation decisions. The SMC will decide whether or not to escalate the dose of avelumab to the next level, or whether an interim dose level will be added by reviewing the safety data after all subjects of a cohort have completed the DLT observation period (see Section 2.1 and SMC Charter).

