### 5.1.3.1 Adverse Drug Reactions Requiring Treatment Discontinuation or Modifications

The following adverse drug reactions (ADRs) require permanent discontinuation or treatment modification of avelumab treatment:

- Any Grade 4 ADRs: permanently discontinue avelumab except for laboratory values out of normal range that do not have any clinical correlation.
- Any Grade 3 ADRs:
  - Withhold avelumab except for laboratory values out of normal range that do not have any clinical correlate.
  - Permanently discontinue avelumab if toxicity does not resolve to Grade  $\leq 1$  or baseline within 12 weeks of last administration or if the same Grade 3 toxicity recurs (consider consult with the medical monitor before permanently discontinuing the treatment).
- Infusion should not be given if ECOG performance status is  $\geq 3$  on the day of study treatment administration. Treatment should be discontinued if ECOG performance status has not improved to  $\leq 2$  by the next scheduled treatment administration.
- Any Grade 2 ADRs should be managed as follows:
  - Infusion should not be given in case of ongoing Grade 2 ADR on the day of study treatment administration.
  - Treatment can be resumed according to original schedule\* once ADR resolved to Grade  $\leq 1$ . Up to 2 subsequent study drug doses may be omitted. If more than 2 doses are skipped, treatment may be resumed after consultation with the Medical Monitor.

\*Original schedule is defined as “the dosing schedule calculated according to first dose”.

If dosing is delayed more than 4 weeks, treatment may be resumed after consultation with the study Medical Monitor. Any delay in dosing in excess of 12 weeks is not permitted.

Infusion-related reactions and irAEs should be handled according to the guidelines provided in Sections 6.5.5.1 and 6.5.5.2, respectively.

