
Grade 3 to 4 Grade 3: Covering > 30% body surface area; Grade 4: Life-threatening consequences
	
Withhold avelumab for Grade 3. Permanently discontinue for Grade 4 or recurrent Grade 3 Consider skin biopsy Dermatology consult 1.0 to 2.0 mg/kg/day prednisone or equivalent Add prophylactic antibiotics for opportunistic infections
	
If improves to Grade 1: Taper steroids over at least 1 month; resume avelumab therapy following steroids taper (for initial Grade 3)

Pulmonary irAEs		
Grade of Pneumonitis (NCI-CTCAE v4.03)	Initial Management	Follow-up Management

Grade 1 Radiographic changes only
	
Consider withholding avelumab therapy Monitor for symptoms every 2 to 3 days Consider Pulmonary and Infectious Disease consults
	
Re-assess at least every 3 weeks If worsens: treat as Grade 2 or Grade 3 to 4

Grade 2 Mild to moderate new symptoms
	
Withhold avelumab therapy Pulmonary and Infectious Disease consults Monitor symptoms daily, consider hospitalization 1.0 to 2.0 mg/kg/day prednisone or equivalent Add prophylactic antibiotics for opportunistic infections Consider bronchoscopy, lung biopsy
	
Re-assess every 1 to 3 days If improves: When symptoms return to Grade ≤ 1, taper steroids over at least 1 month, and then resume avelumab therapy following steroids taper If not improving after 2 weeks or worsening: treat as Grade 3 to 4

Grade 3 to 4 Grade 3: Severe new symptoms; New/worsening hypoxia; Grade 4: life-threatening
	
Permanently discontinue avelumab therapy Hospitalize Pulmonary and Infectious Disease consults 1.0 to 2.0 mg/kg/day prednisone or equivalent Add prophylactic antibiotics for opportunistic infections Consider bronchoscopy, lung biopsy
	
If improves to Grade ≤ 1: taper steroids over at least 1 month If not improving after 48 hours or worsening: add additional immunosuppression (eg, infliximab, cyclophosphamide, iv immunoglobulin, or mycophenolate mofetil)

Hepatic irAEs		
Grade of Liver Test Elevation (NCI-CTCAE v4.03)	Initial Management	Follow-up Management

Grade 1 Grade 1 AST or ALT > ULN to 3.0 x ULN and/or total bilirubin > ULN to 1.5 x ULN
	
Continue avelumab therapy
	
Continue liver function monitoring If worsens: treat as Grade 2 or 3 to 4

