Grade 2 AST or ALT > 3.0 to ≤ 5 × ULN and/or total bilirubin > 1.5 to ≤ 3 × ULN	Withhold avelumab therapy Increase frequency of monitoring to every 3 days	If returns to Grade ≤ 1: Resume routine monitoring; resume avelumab therapy If elevation persists > 5 to 7 days or worsens: Treat as Grade 3 to 4
Grade 3 to 4 AST or ALT > 5 × ULN and /or total bilirubin > 3 × ULN	Permanently discontinue avelumab therapy Increase frequency of monitoring to every 1 to 2 days 1.0 to 2.0 mg/kg/day prednisone or equivalent Add prophylactic antibiotics for opportunistic infections Consult gastroenterologist/hepatologist Consider obtaining MRI/CT scan of liver and liver biopsy if clinically warranted	If returns to Grade ≤ 1: taper steroids over at least 1 month If does not improve in > 3 to 5 days, worsens or rebounds: add mycophenolate mofetil 1 g twice daily If no response within an additional 3 to 5 days, consider other immunosuppressants per local guidelines
Renal irAEs		
Grade of Creatinine Increased (NCI-CTCAE v4.03)	Initial Management	Follow-up Management
Grade 1 Creatinine increased > ULN to 1.5 × ULN	Continue avelumab therapy	Continue renal function monitoring If worsens: Treat as Grade 2 to 3 or 4
Grade 2 to 3 Creatinine increased > 1.5 and ≤ 6 × ULN	Withhold avelumab therapy Increase frequency of monitoring to every 3 days 1.0 to 2.0 mg/kg/day prednisone or equivalent. Add prophylactic antibiotics for opportunistic infections Consider renal biopsy	If returns to Grade ≤ 1: Taper steroids over at least 1 month, and resume avelumab therapy following steroids taper. If worsens: Treat as Grade 4.
Grade 4 Creatinine increased > 6 × ULN	Permanently discontinue avelumab therapy Monitor creatinine daily 1.0 to 2.0 mg/kg/day prednisone or equivalent. Add prophylactic antibiotics for opportunistic infections Consider renal biopsy Nephrology consult	If returns to Grade ≤ 1: Taper steroids over at least 1 month
Cardiac irAEs		
Myocarditis	Initial Management	Follow-up Management

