
Hypopituitarism/Hypophysitis (secondary endocrinopathies)
	
If secondary thyroid and/or adrenal insufficiency is confirmed (ie, subnormal serum FT4 with inappropriately low TSH and/or low serum cortisol with inappropriately low ACTH):
 
 
Refer to endocrinologist for dynamic testing as indicated and measurement of other hormones (FSH, LH, GH/IGF-1, PRL, testosterone in men, estrogens in women)
 
Hormone replacement/suppressive therapy as appropriate
 
Perform pituitary MRI and visual field examination as indicated
 
 
If hypophysitis confirmed:
 
 
Continue avelumab if mild symptoms with normal MRI. Repeat the MRI in 1 month
 
Withhold avelumab if moderate, severe symptoms or life-threatening symptoms of hypophysitis and/or abnormal MRI. Consider hospitalization. Initiate corticosteroids (1 to 2 mg/kg/day prednisone or equivalent) followed by corticosteroids taper during at least 1 month
 
Add prophylactic antibiotics for opportunistic infections
 
	
Resume avelumab once symptoms and hormone tests improve to Grade <math>\leq</math> 1 (with or without hormone replacement).
 
In addition, for hypophysitis with abnormal MRI, resume avelumab only once shrinkage of the pituitary gland on MRI/CT scan is documented.
 
Continue hormone replacement/suppression therapy as appropriate.

Other irAEs (not described above)
		

Grade of other irAEs (NCI-CTCAE v4.03)
	
Initial Management
	
Follow-up Management

Grade 2 or Grade 3 clinical signs or symptoms suggestive of a potential irAE
	
Withhold avelumab therapy pending clinical investigation
	
If irAE is ruled out, manage as appropriate according to the diagnosis and consider re-starting avelumab therapy If irAE is confirmed, treat as Grade 2 or 3 irAE

Grade 2 irAE or first occurrence of Grade 3 irAE
	
Withhold avelumab therapy 1.0 to 2.0 mg/kg/day prednisone or equivalent Add prophylactic antibiotics for opportunistic infections Specialty consult as appropriate
	
If improves to Grade <math>\leq</math> 1: Taper steroids over at least 1 month and resume avelumab therapy following steroids taper

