## 8.4 Analysis Sets

- **Screening Analysis Set:** all subjects who signed the ICF(s).
- **DLT Analysis Set:** all subjects with data used for implementing the dose-escalation schedule (excluding 6 subjects in 10 mg/kg once weekly cohort). These subjects should have received all avelumab administrations in the DLT observation period (first 21 days of treatment) or should have stopped treatment because of DLTs in the DLT observation period.
- **Safety Analysis Set:** all subjects who have received at least 1 dose of avelumab. The Safety Analysis Set will be used for all analyses of safety and efficacy.
- **Efficacy Population:** all subjects who have received at least 1 dose of avelumab and have measurable disease at baseline according to Investigator assessment.
- **PK Analysis Set:** all subjects who have completed at least 1 infusion of avelumab, and who have provided valid PK samples.

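### The DLT Analysis Set and the replacement rule, as written, leave out a subject whose DLT led to a withheld second dose, although the escalation rule counts that subject

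*Protocol*

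**What the plan says.** Protocol Section 8.4 opens the definition of the DLT Analysis Set with subjects whose data drive dose escalation, leaving out the once weekly cohort. It then states that they "should have received all avelumab administrations in the DLT observation period (first 21 days of treatment) or should have stopped treatment because of DLTs" within that period. SAP Section 8.2 repeats this word for word. Protocol Section 8.5.2.1 and SAP Section 15.1 compute the primary DLT number and proportion on this set.

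Section 5.1.1.1 allows replacement of a subject who does not meet the requirement for dose determination. That requirement is met when the subject has had two doses on schedule and "completes the minimal 21-day safety observation period (DLT observation period) unless they discontinue due to a DLT".

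The escalation rule in Section 5.1.2.1.2 has no dosing condition. For 10 mg/kg every 2 weeks the dose is considered safe on this test: "If less than 2 out of the 6 subjects in this cohort experience a DLT". With two or more, the study goes on hold. The text with Figure 5-3 has the SMC decide by "reviewing the safety data after all subjects of a cohort have completed the DLT observation period".

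Section 7.4.1.1 defines a DLT by grade, relatedness and timing, with listed exceptions. It does not require treatment to stop. The general instruction for a Grade 3 adverse drug reaction in Section 5.1.3.1 is "Withhold avelumab except for laboratory values out of normal range that do not have any clinical correlate". Permanent discontinuation follows only if the event does not resolve within 12 weeks or recurs. For a first Grade 3 event in the residual irAE category of Table 6-2, avelumab is withheld and the follow-up on improvement is "Taper steroids over at least 1 month and resume avelumab therapy following steroids taper".

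**The concern.** The two ways into the analysis set do not cover every DLT. A Grade 3 event that starts before the second infusion and is managed by withholding leaves the subject short of a dose, so the first condition fails. Treatment has not been stopped, so the second fails too. The subject leaves the primary analysis because of the very event being counted.

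The resulting error has a direction. Removing such a subject cannot raise the DLT proportion. It leaves it unchanged only if a replacement also has a DLT or if everyone in the cohort had one. With three to six subjects per dose level, one subject can decide the result. The same cohort can also be read as on hold under Section 5.1.2.1.2 and as acceptable under Sections 5.1.1.1 and 8.4.

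**Working it through.** **1. The rules side by side**

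| Place | Who counts |
|---|---|
| Protocol 8.4, SAP 8.2 | all doses in 21 days, or stopped because of a DLT |
| Protocol 5.1.1.1 | 2 doses and 21 days, or discontinued because of a DLT; others may be replaced |
| Protocol 5.1.2.1.2 | any subject who has a DLT |

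**2. One case traced through the text.** Grade 3 rash starts before the second infusion (Day 15, window -3/+1 days in Table 1-1) and has not resolved to Grade 1 or less in under 7 days of medical management.
- Section 7.4.1.1: the skin-toxicity exception does not apply, so this is a DLT.
- Table 6-2, dermatological: withhold for Grade 3, and resume an initial Grade 3 case only after a steroid taper of at least 1 month.
- The second dose is therefore missed and treatment is not stopped. Neither condition in Section 8.4 is met, and Section 5.1.1.1 allows replacement.

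**3. How far the gap reaches**
- Inside: Grade 3 rash as above; Grade 3 creatinine (Table 6-2, renal: "Taper steroids over at least 1 month, and resume avelumab therapy following steroids taper"); first Grade 3 irAEs in the residual category.
- Possibly inside: Grade 3 endocrine events, and other Grade 3 reactions under Section 5.1.3.1, if unresolved at the second dose.
- Outside: Grade 3 pneumonitis, hepatic irAEs and infusion reactions, and most Grade 4 reactions (all permanent discontinuation); Grade 3 diarrhea (a DLT only if treatment is to be discontinued); any DLT starting after the second dose.

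**4. Cohort sizes.** The plan gives no DLT rate, alpha or power. Its only related figure is the planned number of subjects, which reproduces: 3 + 6 + 6 + 6 = 21, and 6 + 6 + 6 + 6 = 24 if the 3 mg/kg cohort is expanded.

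**5. Effect on the reported proportion.** With x DLTs in n subjects, dropping one gap subject gives (x-1)/(n-1), or (x-1)/n if replaced by a subject without a DLT.

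| All DLTs counted | Dropped, not replaced | Replaced, no DLT |
|---|---|---|
| 1/3 = 33.3% | 0/2 = 0% | 0/3 = 0% |
| 1/6 = 16.7% | 0/5 = 0% | 0/6 = 0% |
| 2/6 = 33.3% | 1/5 = 20.0% | 1/6 = 16.7% |

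In the last row Section 5.1.2.1.2 calls for a hold, while the analysis set shows one DLT.

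**6. Upper bound on the escalation effect.** Let p be the true DLT risk and f the share of DLTs in the gap. The documents give neither, so both are assumptions. If every gap subject is replaced, the DLT rate among evaluable subjects is q = p(1-f)/(1-pf). For the six-subject rule, P(fewer than 2 DLTs) = (1-q)^6 + 6q(1-q)^5.

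Example: p = 0.33, f = 0.10 gives q = 0.297/0.967 = 0.307 and P = 0.405, against 0.358 at f = 0.

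| p | f = 0 | 0.05 | 0.10 | 0.25 | 0.50 |
|---|---|---|---|---|---|
| 0.05 | 0.967 | 0.970 | 0.973 | 0.980 | 0.991 |
| 0.10 | 0.886 | 0.895 | 0.903 | 0.928 | 0.964 |
| 0.20 | 0.655 | 0.675 | 0.695 | 0.758 | 0.863 |
| 0.33 | 0.358 | 0.381 | 0.405 | 0.488 | 0.661 |

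Under staggered 3 + 3 enrolment, P = (1-q)^3 + 3q(1-q)^5. At p = 0.33 this runs 43%, 46%, 48%, 56%, 71% over the same values of f.

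**The case against.** **The lead clause already admits the subject.** If the SMC counted the DLT, the subject's data were used for escalation. This does not settle it. The DLT footnote to Table 1-1 ties data used for escalation to dose determination, and Section 5.1.1.1 confines that to two doses plus 21 days or discontinuation for a DLT. At best the definition's two sentences disagree.

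**Stopped may include withheld.** The protocol often writes permanently discontinue where it means that, and it uses stop and discontinue for temporary interruptions of an infusion. The lenient reading is possible but stated nowhere. Section 5.1.3.1 separates withholding from permanent discontinuation, and SAP Section 15.2 treats adverse events leading to treatment discontinuation as permanent.

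**Escalation is protected.** Section 5.1.1.1 permits replacement without ordering it, the SMC reviews the safety data, and Section 5.1.2.1.2 counts every DLT. The SMC Charter, which sets the committee's procedures, is not among the documents. This stands: an effect on escalation is possible, not established, and the table in step 6 is a bound.

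**The case is rare and visible.** This also stands. The subset is narrow, and the largest shifts need p and f values that nothing in the documents supports. Section 5.2.2 describes avelumab as well tolerated from 1 to 20 mg/kg. The analysis is descriptive, and the events remain in the Safety Analysis Set tables. None of this justifies a definition that drops a subject for having the primary event.

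**Conclusion.** The concern holds. Read literally, Protocol Sections 8.4 and 5.1.1.1 and SAP Section 8.2 leave out a subject whose DLT before the second infusion led to a withheld dose, and they conflict with Section 5.1.2.1.2.

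The direct consequence is for the reported primary proportion in that subset: 2/6 becomes 1/5 or 1/6, and 1/3 becomes 0/2 or 0/3, the second figure in each pair assuming a replacement without a DLT. These are constructed counts, but they need no assumed rate.

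The effect on escalation depends on literal use of the replacement rule and on the unknown p and f. With f of 0.05 to 0.10 and every gap subject replaced, the chance of passing the six-subject rule rises by under 1 point at p = 0.05 and by about 2 to 5 points at p = 0.33. The point should be fixed. Confidence is medium, because the subset is narrow and a lenient reading of the wording is available.

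**What to change.** In Protocol Section 8.4 and SAP Section 8.2, keep the lead clause and the exclusion of the once weekly cohort. Keeping the lead clause also keeps out the 20 mg/kg subjects who are added only for PK. Replace the second sentence with:

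*These subjects either received every planned administration and completed the 21-day DLT observation period, or had an SMC-confirmed DLT within it, regardless of whether later dosing was given, withheld, delayed or stopped.*

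In Section 5.1.1.1, change the exception from discontinuing because of a DLT to experiencing a DLT, so that no subject with a DLT is replaced and the rule agrees with Section 5.1.2.1.2.

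The cost is one sentence in each of three places. No subjects, visits or data are added, the planned number of subjects is unaffected, and no dosing or withholding rule changes. The only downside is that the reported DLT proportion may be slightly less favourable.

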## 8.5 Description of Statistical Analyses

### 8.5.1 General Considerations

All data recorded during the study will be presented in individual data listings for the Safety Analysis Set. Unless otherwise specified, all data will be evaluated as observed, and no imputation method for missing values will be used. All data will be presented in a descriptive manner.

Descriptive statistics will be used to summarize the study results, ie, statistics for continuous variables may include means, medians, ranges, and appropriate measures of variability. Qualitative variables will be summarized by counts and percentages. The uncertainty of estimates will be assessed by CIs. Unless otherwise specified, the calculation of proportions will be based on the sample size of the population of interest. Counts of missing observations will be included in the denominator and presented as a separate category if not otherwise specified in the SAP.

Full details of the planned analyses will be provided in the SAP.

### 8.5.2 Analysis of Primary Endpoints

#### 8.5.2.1 DLTs in Dose Escalation Cohorts

DLT is defined in Section 7.4.1.1. The number and proportion of subjects experiencing DLTs will be reported by dose level based on the DLT Analysis Set (excluding 10 mg/kg once weekly cohort).

### 8.5.2.2 Pharmacokinetics Profile

Serum concentrations of avelumab will be determined by a validated method at the time points described in the Schedule of Assessments (Table 1-3, Table 1-4, and Table 1-5).

The PK parameters to be estimated and reported for the PK Analysis Set are defined in Section 7.5.1.

The PK parameters will be summarized using descriptive statistics. Additional PK analysis/display may be generated at the discretion of the pharmacokineticist.

